9.2.12.9 Suicidality Assessment

The profound cognitive impairment of patients with RTT is such that the Children's Columbia-Suicide Severity Rating Scale is not considered appropriate in this trial. Instead, suicidality will be assessed by the investigator via a clinical interview with the caregiver (see [Appendix 3.8](#)).

9.2.13 Tanner Staging

The pubic hair growth and breast development of all adolescent patients (i.e., ≥ 7 years of age⁷¹ at the time of signing the ICF or earlier, if clinically indicated by the onset of menarche or other signs of precocious puberty) will be assessed using Tanner Staging (see [Appendix 3.6](#)).⁷² The assessment can either be performed by examination during the study visit or the appropriate Tanner Stage can be indicated by the caregiver, with reference to the chart provided.'

Once a patient reaches a score of V (i.e., 5) the assessment need not be performed again.

9.2.14 Investigational Medicinal Product Accountability

Records of GWP42003-P accountability will be maintained according to [Section 5.2.4](#).

GWP42003-P will be dispensed at each of the following visits:

Study Code: GWND19002
EudraCT Number: 2019-001605-24
Clinical Protocol V1 09Aug19

- Visit 1 (Day 1)
- Visit 4 (Day 29)
- Visit 5 (Day 57)
- Visit 6 (Day 85)
- Visit 7 (Day 141)
- Visit 8 (Day 197)

Caregivers will be asked to return all GWP42003-P (used and unused) at each relevant visit (Visits 4, 5, 6, 7, 8, and 9). The center will check the returned GWP42003-P against the expected usage. Any discrepancies will be discussed with the caregiver at the time of the visit and documented accordingly within the patient's source documents.

9.2.15 Adverse Events

All AEs (including SAEs) occurring during the trial will be reported on the running logs in the AE section of the eCRF. This includes all events from the time following screening (Visit 1) up to and including the post-trial follow-up visit (Visit 10), whether or not attributed to GWP42003-P and observed by the investigator or patient.

* For the patient's expected seizure types, these do not routinely require documentation as AEs. However, any worsening, including a change in the pattern or severity of seizures should be documented in the eCRF if deemed to meet the definition of an AE, in the investigator's opinion.

Any AE that meets SAE criteria should still be reported as a SAE.

Serious adverse events must be reported to GW Pharmacovigilance Department (PVD) within 24 hours of discovery or notification of the event via recording in the eCRF.

Refer to [Section 12](#) for definitions, procedures, and further information on AE reporting.

Study Code: GWND19002
 EudraCT Number: 2019-001605-24
 Clinical Protocol V1 09Aug19

10 IMP WITHDRAWAL

In accordance with the Declaration of Helsinki⁷³ the International Council for Harmonisation (ICH) Harmonised Guideline: Integrated Addendum to ICH E6(R1): Guideline for Good Clinical Practice (GCP) E6(R2)⁷⁴ the FDA regulations relating to GCP and clinical trials^{75,76,77} the EU Clinical Trials Directive⁷⁸ the EU GCP Directive⁷⁹ and/or other applicable regulations, a patient has the right to withdraw from the trial at any time and for any reason, with no obligation to provide a reason and without prejudice to her future medical care by the physician or at the institution.

The patient must be withdrawn permanently discontinued from the trial if any of the following apply:

- Administrative decision by the investigator, GW, or a regulatory authority
- Pregnancy
- Protocol deviation that is considered to potentially compromise the safety of the patient
- Withdrawal of patient assent
- Withdrawal of parent(s)/legal representative consent
- ALT or AST $> 3 \times$ ULN with the appearance of fatigue, nausea, vomiting, right upper quadrant pain or tenderness, fever, rash, and/or eosinophilia ($> 5\%$)
- ALT or AST $> 8 \times$ ULN
- ALT or AST $> 5 \times$ ULN for more than 2 weeks
- ALT or AST $> 3 \times$ ULN **and** (total bilirubin [TBL] $> 2 \times$ ULN **or** international normalized ratio [INR] > 1.5)

Note: Prior to withdrawal for the transaminase elevations noted above, the investigator may choose to confirm the transaminase elevations by repeating the following laboratory tests within 24 to 48 hours: ALT, AST, TBL, INR, % eosinophils, gamma-glutamyl transferase, alkaline phosphatase, and eosinophils. **Should the above transaminase elevation criteria be confirmed, the patient must be withdrawn from the trial. In cases where the transaminase elevation withdrawal criteria are not met or confirmed, the dose of IMP or a concomitant medication with known hepatotoxicity may be**

Study Code: GWND19002
EudraCT Number: 2019-001605-24
Clinical Protocol V1 09Aug19

reduced. Dose adjustments should be discussed with the GW medical monitor. The final decision regarding dose adjustments should be taken by the investigator.

- Lost to follow-up

The patient may also be withdrawn permanently from the trial for any of the following:

- Patient or caregiver noncompliance
- AE (including clinically significant laboratory result) that, in the opinion of the investigator, would compromise the continued safe participation of the patient in the trial
- Failure to meet the eligibility criteria
- Any evidence of the use of drugs of abuse or drug diversion
- Suicidal ideation or behavior during the treatment period

The patient should attend a withdrawal visit (Visit 8) as soon as possible after the decision is made to permanently discontinue GWP42003-P. Patients who discontinue the IMP should have their dose of IMP gradually reduced (10% each day) over a period of 10 days, beginning at the time the decision is made to discontinue (unless inadvisable due to an AE). Patients should continue in the trial and continue to complete trial assessments and visits per protocol. Patients who discontinue the IMP and complete tapering of the IMP prior to the completion visit do not need to attend an End of Taper visit.

Should a patient request or decide to withdraw from the trial, all efforts must be made to complete and report the observations as thoroughly as possible up to the date of withdrawal. Patients withdrawing due to an AE should be followed up according to [Section 12.7](#). All information should be reported on the applicable eCRF pages. All assessments required at the withdrawal visit should be conducted, if possible. If the tapered dose is administered, patients should return for Visit 9, if possible. Wherever possible, a safety follow-up visit should take place 28 days from the date of last dose of IMP. If the withdrawing patient declines to give a reason for withdrawal of consent, the investigator must respect the patient's wishes.

Study Code: GWND19002
EudraCT Number: 2019-001605-24
Clinical Protocol V1 09Aug19

11 URGENT SAFETY MEASURES

The sponsor and investigator may take appropriate urgent safety measures in order to protect the patients of a clinical trial against any immediate hazard to their health or safety. If such measures are taken by the investigator, they must notify GW immediately or at least within 24 hours of awareness. GW will report urgent safety measures to regulatory authorities by telephone within 24 hours of awareness, wherever possible, and will provide a written report to the regulatory authorities and IRB/IEC within 3 days.

Study Code: GWND19002
EudraCT Number: 2019-001605-24
Clinical Protocol V1 09Aug19

12 ADVERSE EVENT REPORTING

12.1 Definitions

12.1.1 Adverse Event

For the purposes of this trial, an AE is defined as follows:

Any new unfavorable/unintended signs/symptoms (including abnormal laboratory findings when relevant) or diagnosis or worsening of a pre-existing condition that occurs at any point up to the post-treatment, final safety follow-up visit (Visit 10), which may or may not be considered to be related to GWP42003-P. Any event that is the result of a trial procedure must be recorded as an AE.

Surgical/Investigational procedures are not AEs. The medical reason for the procedure is the AE. Elective hospitalizations for pretrial existing conditions or elective procedures are not AEs. The exception may be if the patient has an AE during hospitalization that prolongs the scheduled hospital stay, in which case it would be considered an SAE (refer to [Section 12.2](#)).

If reporting a fatal event, the SAE term should be the underlying cause of death (e.g., disease or medical condition leading to death).

12.1.2 Investigator

The term “investigator” refers to the trial principal investigator (PI) or a formally delegated trial physician.

12.2 Serious Adverse Events

During clinical investigations, AEs may occur, which if suspected to be GWP42003-P-related, might be significant enough to lead to important changes in the way GWP42003-P is developed (e.g., change in dose, population, monitoring need, consent/assent forms). This is particularly true for events that threaten life or function. Such SAEs will be reported promptly to regulatory authorities, applicable IRBs/IECs, and investigators (expedited reporting) by GW.

An AE must only be classed as serious, i.e., an SAE, when the event falls into one of the following criteria:

- Results in death
- Is life threatening*

Study Code: GWND19002
EudraCT Number: 2019-001605-24
Clinical Protocol V1 09Aug19

- Requires inpatient hospitalization or prolongation of existing hospitalization
- Results in persistent or significant disability/incapacity
- Is a congenital anomaly/birth defect
- Is medically significant**

* The term “life threatening” in the definition of “serious” refers to an event in which the patient was at risk of death at the time of the event; it does not refer to an event that, hypothetically, might have caused death if it were more severe.

** Medical and scientific judgment should be exercised in deciding whether SAE reporting is appropriate in other situations. Important medical events may not be immediately life threatening or result in death or hospitalization but may jeopardize the patient or may require intervention to prevent one of the other outcomes listed in the definition above. These should also usually be considered serious. Examples of such events are intensive treatment in an emergency room or at home for allergic bronchospasm, blood dyscrasias or convulsions that do not result in hospitalization, or development of drug dependency or use of drugs of abuse.

12.3 Reporting Procedures for Serious Adverse Events

All SAEs occurring during the trial must be reported to GW with any other supporting information and recorded in the AE section of the eCRF. Any ongoing SAEs should be followed up until resolution, wherever possible. For all deaths, the working diagnosis or cause of death as stated on a death certificate, available autopsy reports, and relevant medical reports should be sent to GW promptly.

All SAEs must be recorded in the eCRF within 24 hours of discovery or notification of the event. GW Research Ltd PVD will be automatically notified that an SAE has been recorded. Any additional information required for a case (follow-up or corrections to the original case) will be requested by GW PVD through eCRF queries.

The investigator should continue to document all AEs that occur up to the last formal follow-up observational period (Visit 10). If the investigator subsequently becomes aware of any deaths or a new GWP42003-P-related SAE after the last formal follow-up period of the trial, these should still be reported to GW PVD.

Any other problem discovered after Visit 10 that is deemed to be an unexpected safety issue and is likely to have an impact on patients who have taken part in the trial must be

Study Code: GWND19002
EudraCT Number: 2019-001605-24
Clinical Protocol V1 09Aug19

treated as an SAE and reported to GW PVD. Such post-trial SAEs do not need to be recorded on the patient's eCRF if editing rights to the eCRF have been removed due to the final trial data lock. GW Research Ltd PVD may request safety follow-up information after the final trial visit in order to investigate a potential safety issue.

Contact details for GW PVD are provided at the front of the center files for all trial centers.

12.4 Pregnancy

Any patient who has become pregnant while receiving GWP42003-P or within 90 days of the last dose of GWP42003-P must be reported to GW PVD. Where possible, the investigator should provide the outcome of the pregnancy.

All pregnancies must be recorded in the eCRF within 24 hours of awareness. GW PVD will be automatically notified that a pregnancy has been recorded. Any additional information required for a case (follow-up or corrections to the original case) will be requested by GW PVD through eCRF queries.

The investigator is not obliged to actively monitor for any pregnancies that commence more than 90 days after the final dose of GWP42003-P. However, if the investigator becomes aware of a new pregnancy outside this time limit, then he/she should report it as above. GW PVD will follow up for all pregnancy outcomes.

12.5 Causality Assessment

Causality assessment is required for all AEs and SAEs. Causality assessment must only be assigned by the investigator. All cases judged as having a reasonable suspected causal relationship to GWP42003-P must be reported as such. The expression "*reasonable causal relationship*" is meant to convey in general that there are facts (evidence) or arguments to suggest a causal relationship.

The following question, which must be answered by the investigator for all AEs, is used to capture the reasonable causal relationship of an event to GWP42003-P:

"In your opinion, is there a plausible relationship to the IMP?" The answer is either "yes" or "no."

Events that start before the first dose of the IMP (pretreatment) should be considered as not causally related. Where a pretreatment event worsens in severity following the first dose of the IMP, a new event record should be entered into the eCRF.

Study Code: GWND19002
EudraCT Number: 2019-001605-24
Clinical Protocol V1 09Aug19

Considering the explanation given above, investigators are strongly encouraged to express their opinion on what the cause of an AE might be. For individual patients, the investigator is usually in the best position to assess the underlying suspected cause of an AE. For all AEs, especially SAEs, it is important that the investigator assess not only the possible role of GWP42003-P but also other potential contributing factors. Factors for consideration of the underlying cause may include the following:

- Medical and disease history
- Lack of efficacy/worsening of treated condition
- Concomitant or previous treatment
- IMP discontinuation
- Protocol-related procedure

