- Continuing
- Patient died

D) Severity

When describing the severity of an AE, the terms mild, moderate, or severe should be used. Clinical judgment should be used when determining which severity applies to any AE.

If the severity of an AE fluctuates day to day, e.g., a headache or constipation, the change in severity should not be recorded each time; instead, only the worst observed severity should be recorded, with the AE start and stop dates relating to the overall event duration, regardless of severity.

A severe AE is not the same as an SAE. For example, a patient may have severe vomiting, but the event does not result in any of the SAE criteria above. Therefore, it should not be classified as serious.

E) Causality

See [Section 12.5](#).

Study Code: GWND19002
EudraCT Number: 2019-001605-24
Clinical Protocol V1 09Aug19

F) Action Taken with IMP

This question refers to the action taken with GWP42003-P due to an AE. The action with GWP42003-P must be classified as follows:

- None
- Dose reduced temporarily
- Dose reduced
- IMP interrupted
- IMP stopped

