13.6.2.2 Adverse Events

AEs will be coded according to the Medical Dictionary for Regulatory Activities dictionary.

A treatment-emergent adverse event (TEAE) is one that started or worsened in severity or seriousness following the first dose of IMP.

Descriptive presentations of TEAEs will be given by preferred term and system organ class for the safety analysis set. The number of patients reporting at least 1 TEAE will be provided.

The following summaries will be produced as a minimum:

- All-causality TEAEs.
- Treatment-related AEs.
- All-causality TEAEs by maximal severity.
- All-causality serious TEAEs.
- Treatment-related serious TEAEs.
- TEAEs reported as leading to permanent cessation of IMP.
- Fatal TEAEs.

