12.5 Causality Assessment

Causality assessment is required for all AEs and SAEs. Causality assessment must only be assigned by the investigator. All cases judged as having a reasonable suspected causal relationship to GWP42003-P must be reported as such. The expression "*reasonable causal relationship*" is meant to convey in general that there are facts (evidence) or arguments to suggest a causal relationship.

The following question, which must be answered by the investigator for all AEs, is used to capture the reasonable causal relationship of an event to GWP42003-P:

"In your opinion, is there a plausible relationship to the IMP?" The answer is either "yes" or "no."

Events that start before the first dose of the IMP (pretreatment) should be considered as not causally related. Where a pretreatment event worsens in severity following the first dose of the IMP, a new event record should be entered into the eCRF.

Study Code: GWND19002
EudraCT Number: 2019-001605-24
Clinical Protocol V2 18Dec19

Considering the explanation given above, investigators are strongly encouraged to express their opinion on what the cause of an AE might be. For individual patients, the investigator is usually in the best position to assess the underlying suspected cause of an AE. For all AEs, especially SAEs, it is important that the investigator assess not only the possible role of GWP42003-P but also other potential contributing factors. Factors for consideration of the underlying cause may include the following:

- Medical and disease history
- Lack of efficacy/worsening of treated condition
- Concomitant or previous treatment
- IMP discontinuation
- Protocol-related procedure

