6.1.8.1 Adverse events

Any adverse events occurring between last dose of RCT and OLE visit 1 will not be considered Treatment Emergent Adverse events (Aes occurring during study break). All other adverse events will be considered as treatment-emergent adverse events.

A TEAE will be considered treatment-related if the plausibility relationship to IMP is recorded on the eCRF as 'yes'. If the data on plausibility relationship to IMP is missing then the TEAE will be considered treatment-related.

A TEAE will be considered leading to permanent discontinuation of IMP (leading to withdrawal) if the action taken with IMP is recorded on the eCRF as 'trial medication stopped' or the outcome is recorded on the eCRF as 'patient died'.

A treatment-related TEAEs leading to withdrawal is a TEAE leading to permanent IMP discontinuation and considered treatment-related as per above definition.

A TEAE will be considered leading to IMP temporary discontinuation if the action taken with IMP is recorded on the eCRF as 'trial medication interrupted'.

A TEAE will be considered leading to permanent IMP dose reduction excluding permanent discontinuation if the action taken with IMP is recorded on the eCRF as 'dose reduced'.

A TEAE will be considered fatal if the outcome is recorded on the eCRF as 'patient died'.

The time to first onset of AE will be calculated for TEAEs as:

$$\text{Start date of AE} - \text{Day 1} + 1$$

The time to AE resolution will be calculated for TEAEs as:

$$\text{Stop date of AE} - \text{Start date of AE} + 1$$

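### The rule for opening a new adverse event record names worsening in severity only, so an event from the RCT-to-OLE break that turns serious on drug can be missing from the serious TEAE tables

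*Protocol*

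**What the plan says.** Three rules decide whether an event that straddles the first OLE dose is counted. The protocol wording is the same in V1 and V2.

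- **Recording, protocol 12.5.** "Where a pretreatment event worsens in severity following the first dose of the IMP, a new event record should be entered into the eCRF". Seriousness is not named. The same section adds: "Events that start before the first dose of the IMP (pretreatment) should be considered as not causally related".
- **Definition, protocol 13.6.2.2.** A TEAE is "one that started or worsened in severity or seriousness following the first dose of IMP". There are two worsening triggers here.
- **Derivation, SAP 6.1.8.1.** "Any adverse events occurring between last dose of RCT and OLE visit 1 will not be considered Treatment Emergent Adverse events". Then: "All other adverse events will be considered as treatment-emergent adverse events". Neither sentence has a worsening clause.

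Protocol 12.6 keeps severity and seriousness apart: "A severe AE is not the same as an SAE". It grades severity as mild, moderate or severe. Among the items required for each event it lists start and stop dates, but no date on which the event became serious.

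Serious TEAEs and treatment-related serious TEAEs are named summaries in both protocol 13.6.2.2 and SAP 9.1. SAP 9.5, which describes changes from the protocol analysis, names the added OLE-baseline comparison but not the altered TEAE rule.

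**The concern.** The definition has two triggers and the recording rule has one. A new record with a post-dose start date is the only thing in the listed adverse event items that shows an earlier event got worse on drug. If none is opened, the analyst sees one record that starts before the first OLE dose, and the SAP excludes it when that start lies in the break.

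The gap is not just a matter of grading habits. An event already rated severe has no higher grade to reach, so 12.5 can never call for a new record for it. Seriousness is then the only way it can worsen under the TEAE definition, and it is the one that 12.5 omits. The protocol's own illustration in 12.6, severe but non-serious vomiting, is such an event.

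Long-term safety is the primary objective, and the serious TEAE summaries are among its core outputs. An admission to hospital on GWP42003-P that is absent from them is a miscount where it matters most.

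**Working it through.** The plan gives no figure to reproduce and the trial is descriptive, so the check is to trace events through the three rules.

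| Event | Record under protocol 12.5 | TEAE by protocol 13.6.2.2 | TEAE by SAP 6.1.8.1 |
|---|---|---|---|
| A. Starts in the break, severity grade rises after first OLE dose | New record required, post-dose start | Yes | Yes |
| B. Starts in the break, becomes serious after first OLE dose, grade unchanged, old record updated | No new record required | Yes | **No** |
| C. As B, but the site opens a new record anyway | Not required, not forbidden | Yes | Yes |
| D. Starts up to the last RCT dose, becomes serious on OLE drug | No new record required | Yes | Yes, by the second SAP sentence |
| E. Starts on the day of OLE Visit 1 | Not decisive | Yes if post-dose | Yes; SAP 6.1.6.1.3 assumes such events are post-dose |

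Only row B is lost.

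**Illustration (hypothetical).** A moderate, non-serious infection starts 5 days before OLE Visit 1 and leads to hospitalisation on OLE Day 10, still rated moderate. The protocol definition gives 1 serious TEAE. The SAP gives 0 if the old record is updated and 1 if a new record is opened. The count depends on a site choice that neither document settles.

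**Causality in row B.** Because the record starts before the first OLE dose, 12.5 directs sites to call it unrelated. SAP 6.1.8.1 classes a TEAE as treatment-related only when the relationship is recorded as yes or is missing. So even if the SAP readmitted the event, it would still be absent from the treatment-related serious summary.

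**Recoverability.** With no date of becoming serious among the listed items, the protocol definition cannot be applied to row B from those items alone.

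**Length of the break.** The SAP counts from the last RCT dose. The RCT protocol is not among the documents, so assume its follow-up is timed as here. In this trial the taper ends on Day 739 and follow-up is on Day 767:

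- Entry at RCT Visit 11: 767 − 739 = 28 days.
- Entry at RCT Visit 11 with the 7-day window that this protocol allows for its own follow-up call: 28 + 7 = 35 days.
- Entry on the day of RCT Visit 9, as recommended: near 0.
- Entry under annex version 2 after RCT Visit 11: longer, with no upper limit stated.

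**The case against.** The strongest reply is that nothing need be lost. Protocol 12.1.1 treats worsening of an existing condition as an adverse event in its own right, 12.6 starts OLE recording at Visit 1, and 12.5 does not forbid a new record. A site could properly enter the admission as a new on-drug event. That stands, and it is why the event *can* drop out rather than *will*. It does not close the gap, because the SAP plainly expects records with onset in the break, and sites may handle them differently.

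The safeguards are also real. Protocol 12.3 requires every SAE in the eCRF within 24 hours, with automatic notification of pharmacovigilance. SAP 9.1 provides a separate listing of serious adverse events that is not confined to TEAEs. The event is missing from a summary count, not from the report.

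Four stronger readings are tempting, and the documents do not support them:

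- *Any on-drug worsening of a break-onset event is lost.* Worsening in severity already gets a new post-dose record, which the SAP counts (row A).
- *Section 12.6 contradicts 12.5 by asking that* "only the worst observed severity should be recorded, with the AE start and stop dates relating to the overall event duration". That instruction concerns severity that fluctuates from day to day. Section 12.5 addresses the specific case of a pretreatment event worsening after the first dose, and the two can be read together.
- *The window is 10 + 28 = 38 days.* This counts from RCT Visit 9. The 10 taper days are dosing days, and the SAP's break begins only after the last dose.
- *The TEAE rule always under-counts.* Row B runs toward fewer events. Elsewhere the SAP counts every event outside the break as a TEAE with no worsening test, which can exceed the protocol definition.

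**Conclusion.** The mismatch is real and V2 did not remove it. Following the stated rules can leave an on-drug serious worsening out of the serious TEAE and treatment-related serious TEAE summaries, while the protocol's definition says that it belongs there. The SAP adds to this by dropping the worsening clause without declaring the change.

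The reach is narrow. The event must start in the break, persist past the first OLE dose, become serious with no rise in grade, and receive no new record. No frequency can be derived from the documents. Because same-day entry is recommended and the conditions must coincide, few events are likely to be affected, with delayed and annex entrants the most exposed. The 28-day figure rests on the assumption that the RCT follow-up falls 28 days after the last dose, as it does here. The point deserves correction because it touches a primary safety output and costs almost nothing to repair, not because a large bias is expected.

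**What to change.** 1. **Protocol 12.5 (or the eCRF completion guideline).** Extend the trigger to worsening in severity *or seriousness* after the first dose of IMP *in this trial*. Require the new record to carry the date of worsening, and have causality assessed on it in the normal way.
2. **SAP 6.1.8.1.** Restore the protocol's worsening clause, so that a break-onset event that worsens in severity or seriousness after the first OLE dose counts as a TEAE. If the SAP rule is kept as it is, declare the departure in SAP 9.5.
3. **Data query.** Before database lock, query every SAE whose start date precedes OLE Day 1, to establish when it became serious.

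The SAP change alone is not enough: without a dated new record the analyst cannot see the worsening, and the causality entry stays at unrelated. The cost is one clause in each document and a small query. A few more events may be counted.
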